### **Supplemental Investigations**

- If CR determination depends on a residual lesion that decreased in size but did not disappear completely, it is recommended the residual lesion be investigated with biopsy or fine needle aspirate. If no disease is identified, objective status is CR.
- If progression determination depends on a lesion with an increase possibly due to necrosis, the lesion may be investigated with biopsy or fine needle aspirate to clarify status.

### **Subjective progression**

Patients requiring discontinuation of treatment without objective evidence of disease progression should not be reported as PD on tumor assessment CRFs. This should be indicated on the end of treatment CRF as off treatment due to Global Deterioration of Health Status. Every effort should be made to document objective progression even after discontinuation of treatment.

**Table 1. Objective Response Status at each Evaluation**

Target Lesions	Non-target Disease	New Lesions	Objective status
CR	CR	No	CR
CR	Non-CR/Non-PD	No	PR
CR	Indeterminate or Missing	No	PR
PR	Non-CR/Non-PD, Indeterminate, or Missing	No	PR
SD	Non-CR/Non-PD, Indeterminate, or Missing	No	Stable
Indeterminate or Missing	Non-PD	No	Indeterminate
PD	Any	Yes or No	PD
Any	PD	Yes or No	PD
Any	Any	Yes	PD

**Table 2. Objective Response Status at each Evaluation for Patients with Non-Target Disease Only**

Non-target Disease	New Lesions	Objective status
CR	No	CR
Non-CR/Non-PD	No	Non-CR/Non-PD
Indeterminate	No	Indeterminate
Unequivocal progression	Yes or No	PD
Any	Yes	PD

#### **Appendix 4. Immune-Related Response Criteria Derived from RECIST 1.1 (irRECIST)**

Increasing clinical experience indicates that traditional response criteria may not be sufficient to fully characterize activity in this new era of targeted therapies and/or biologics.

This is particularly true for immunotherapeutic agents such as anti-CTLA4 and anti-PD-1/anti-PD-L1 antibodies which exert the antitumor activity by augmenting activation and proliferation of T cells, thus leading to tumor infiltration by T cells and tumor regression rather than direct cytotoxic effects. Clinical observations of patients with advanced melanoma treated with ipilimumab, for example, suggested that conventional response assessment criteria such as Response Evaluation Criteria in Solid Tumors (RECIST) and WHO criteria are not sufficient to fully characterize patterns of tumor response to immunotherapy because tumors treated with immunotherapeutic agents may show additional response patterns that are not described in these conventional criteria.

Furthermore, the conventional tumor assessment criteria (RECIST and WHO criteria) have been reported as not capturing the existence of a subset of patients who have an OS similar to those who have experienced CR or PR but were flagged as PD by WHO criteria.

On these grounds, a tumor assessment system has been developed that incorporates these delayed or flare-type responses into the RECIST v1.1 (irRECIST).

For irRECIST, only target and measurable lesions are taken into account. In contrast to RECIST v1.1, irRECIST:

- Requires confirmation of progression by imaging at least 4 weeks from the date first documented, and
- Does not necessarily score the appearance of new lesions as progressive disease if the sum of lesion diameters of target lesions (minimum of 10 mm longest diameter per non-nodal lesion and 15 mm shortest diameter per nodal lesion, maximum of 5 target lesions, maximum of 2 per organ) and measurable new lesions does not increase by  $\geq 20\%$ .

The same method of assessment and the same technique should be used to characterize each identified and reported target lesion(s) at baseline and throughout the trial.

irRECIST is defined as follows:

- Overall immune-related complete response (irCR): Complete disappearance of all lesions (whether measurable or not) and no new lesions. All measurable lymph nodes also must have a reduction in short axis to  $<10$  mm.
- Overall immune-related partial response (irPR): Sum of the diameters (longest for non-nodal lesions, shortest for nodal lesions) of target and new measurable lesions decreases  $\geq 30\%$ .

- Overall immune-related stable disease (irSD): Sum of the diameters (longest for non-nodal lesions, shortest for nodal lesions) of target and new measurable lesions is neither irCR, irPR, (compared to baseline) or immune-related progressive disease (irPD, compared to nadir).
- Overall immune-related progressive disease (irPD): Sum of the diameters (longest for non-nodal lesions, shortest for nodal lesions) of target and new measurable lesions increases  $\geq 20\%$  (compared to nadir), confirmed by a repeat, consecutive observation at least 4 weeks from the date first documented.

New measurable lesions: Incorporated into tumor burden (ie, added to the target lesion measurements). A lymph node has to be  $\geq 15$  mm in short axis to be a measurable new lesion and its short axis measurement is included in the sum. Up to 2 new lesions per organ and up to 5 new lesions in total can be added to the measurements.

New non-measurable lesions: Do not define progression but preclude irCR.

Overall responses derived from changes in index, non-index, and new lesions are outlined in Table 8.

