### **Target lesions**

All measurable lesions up to a maximum of 2 lesions per organ, 5 lesions in total, representative of all involved organs, should be identified as target lesions at baseline. Target lesions should be selected on the basis of size (longest lesions) and suitability for accurate repeated measurements. Record the longest diameter for each lesion, except in the case of pathological lymph nodes for which the short axis should be recorded. The sum of the diameters (longest for non-nodal lesions, short axis for nodal lesions) for all target lesions at baseline will be the basis for comparison to assessments performed on study.

- If two target lesions coalesce the measurement of the coalesced mass is used. If a large target lesion splits, the sum of the parts is used.
- Measurements for target lesions that become small should continue to be recorded. If a target lesion becomes too small to measure, 0 mm should be recorded if the lesion is considered to have disappeared; otherwise a default value of 5 mm should be recorded.

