**NOTE: When nodal lesions decrease to <10 mm (normal), the actual measurement should still be recorded.**

### **Non-target disease**

All non-measurable disease is non-target. All measurable lesions not identified as target lesions are also included as non-target disease. Measurements are not required but rather assessments will be expressed as ABSENT, INDETERMINATE, PRESENT/NOT INCREASED, INCREASED. Multiple non-target lesions in one organ may be recorded as a single item on the case report form (eg, 'multiple enlarged pelvic lymph nodes' or 'multiple liver metastases').

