### **Target disease**

- Complete Response (CR): Complete disappearance of all target lesions with the exception of nodal disease. All target nodes must decrease to normal size (short axis <10 mm). All target lesions must be assessed.
- Partial Response (PR): Greater than or equal to 30% decrease under baseline of the sum of diameters of all target measurable lesions. The short diameter is used in the sum for target nodes, while the longest diameter is used in the sum for all other target lesions. All target lesions must be assessed.
- Stable: Does not qualify for CR, PR or Progression. All target lesions must be assessed. Stable can follow PR only in the rare case that the sum increases by less than 20% from the nadir, but enough that a previously documented 30% decrease no longer holds.

- Indeterminate. Progression has not been documented, and
  - One or more target measurable lesions have not been assessed;
  - Or assessment methods used were inconsistent with those used at baseline;
  - Or one or more target lesions cannot be measured accurately (eg, poorly visible unless due to being too small to measure);
  - Or one or more target lesions were excised or irradiated and have not reappeared or increased.

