10.4. Appendix: Immune-related Response Criteria per RECIST 1.1 (irRECIST)

Immune-related progressive disease (irPD) needs to be confirmed by a second, consecutive assessment at least 4 weeks apart. irPD is also considered to be confirmed if the patient:

- dies within 12 weeks after the initial observation of irPD, or
- discontinues treatment due to disease progression (clinical deterioration without radiological documentation) prior to or within 12 weeks after the assessment of irPD.

Immune-related Best Overall Response (irBOR) will be derived based on reported lesion responses at different evaluation time points from the start date until confirmed immune-related disease progression per irRECIST, according to the following rules.

[figure not shown]
- Confirmed irCR = at least two determinations of irCR at least 4 weeks apart before irPD.
- Unconfirmed irCR = one determination of irCR before irPD (and not qualifying for confirmed irCR or irPR).
- Confirmed irPR = at least two determinations of irPR or better at least 4 weeks apart before irPD (and not qualifying for confirmed irCR).
- Unconfirmed irPR = one determination of irPR before irPD (and not qualifying for confirmed irCR or irPR or unconfirmed irCR).
- irSD = at least one irSD or irPD assessment ≥ 6 weeks after start date and before confirmed irPD (and not qualifying for confirmed/unconfirmed irCR or irPR).
- irPD = ≤ 12 weeks after the first dose of study treatment and at least two consecutive determinations of irPD at least 4 weeks apart. irPD is also considered to be confirmed if the patient:
 - dies within 12 weeks after the initial observation of irPD, or
 - discontinues treatment due to disease progression (clinical deterioration without radiological documentation) prior to or within 12 weeks after the assessment of irPD.
- NE: All other cases.

Only tumor assessments performed before the start of any further anti-cancer treatment will be considered in the assessment of irBOR.

Immune-related Objective Response (irOR) is defined as irCR or irPR according to irRECIST from start date until confirmed irPD or death due to any cause. Both irCR and irPR must be confirmed by repeat assessments performed no less than 4 weeks after the criteria for immune-related response are first met. Also, irPD must be confirmed by a

second, consecutive assessment at least 4 weeks apart. Immune-related OR rate (irORR) is the proportion of patients with irOR in the analysis set.

CCI

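### irPD has no minimum absolute increase, so when the nadir sum is below 25 mm a confirmed rise of less than 5 mm can count as progression in irPFS and irDR

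*Protocol*

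**What the plan says.** Protocol Appendix 4 calls irPD when the sum of diameters of "target and new measurable lesions increases" by 20% or more, "compared to nadir), confirmed by a repeat, consecutive observation at least 4 weeks from the date first documented". Table 8 repeats the 20% threshold and adds no millimetre condition. Target lesions enter the sum at 10 mm or more (non-nodal, longest diameter) or 15 mm or more (nodal, short axis), up to five in total and two per organ.

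Both documents require confirmation. SAP 10.4 says "Immune-related progressive disease (irPD) needs to be confirmed by a second, consecutive assessment at least 4 weeks apart". It also treats irPD as confirmed, without a second scan, if the participant "dies within 12 weeks after the initial observation of irPD, or" stops treatment for clinical deterioration in the stated window. SAP 10.4 sets event dates and censoring for irPFS and irDR but gives no absolute minimum.

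Appendix 3 covers shrunken target lesions. If a lesion is still present but too small to measure, "otherwise a default value of 5 mm should be recorded". Nodes are handled differently: "When nodal lesions decrease to <10 mm (normal), the actual measurement should still be recorded".

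**The concern.** A purely relative threshold becomes very small in millimetres when the sum is small. The participants exposed are those with one small target lesion and those whose disease has shrunk most. For them, ordinary variation between readings can exceed 20% of the nadir. The nadir is also the lowest value seen so far, so a single low reading fixes a low reference for every later scan.

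Under SAP 10.4 a confirmed irPD is an irPFS event and ends irDR. Tumour control duration and radiographic PFS by irRECIST are secondary endpoints for Cohort 3B. That cohort has 18 participants, and the inclusion criteria ask for a measurable lesion in at least about 40% of Part B: 0.40 × 18 = 7.2, so about 7. One miscalled participant among 7 is 1/7, or about 14 percentage points of that subset. Appendix 4 presents irRECIST as a way to avoid missing delayed or flare-type responses, so over-calling progression after deep shrinkage works against its purpose.

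**Working it through.** The documents state no error rate for the irPD rule, so there is no figure to reproduce.

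**Threshold in millimetres.** Rise needed = 0.20 × nadir sum.

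| Nadir sum | Rise needed | 1 mm as % of sum |
|---|---|---|
| 5 mm | 1 mm | 20% |
| 10 mm | 2 mm | 10% |
| 15 mm | 3 mm | 6.7% |
| 25 mm | 5 mm | 4% |
| 30 mm | 6 mm | 3.3% |

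The threshold is below 5 mm exactly when the sum is below 5 / 0.20 = 25 mm. If diameters are recorded in whole millimetres, sums of 21 to 24 mm already need 5 mm (0.20 × 21 = 4.2, next whole value 5), so a floor matters at 20 mm or less.

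**Worked case.** Take a single non-nodal lesion of 12 mm at baseline, recorded at the 5 mm default, then read as 6 mm on two consecutive scans. This assumes that the Appendix 3 default carries over to the irRECIST sum, since Appendix 4 does not repeat it. Against nadir: (6 − 5) / 5 = +20%, confirmed. Against baseline: (6 − 12) / 12 = −50%. The participant is confirmed irPD. The same reading also meets the partial-response row of Table 8, which is judged against baseline, and the table states no order of precedence.

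**Illustrative simulation.** Inputs from the documents: the 20% rule, the running nadir, confirmation at the next scan, the entry sizes and 8-weekly scans. Assumed: a true size that never changes, independent normal reading error per lesion, readings rounded to 1 mm, and six post-baseline scans (6 × 8 = 48 weeks). Baseline readings are held at or above entry size. There were 200,000 runs per setting. A case counts when two consecutive scans are each at least 20% above the same nadir.

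| Stable lesion | SD 1.0 | SD 1.5 | SD 2.0 | With 5 mm floor (SD 1.0 / 1.5 / 2.0) |
|---|---|---|---|---|
| One 15 mm node | 7% | 24% | 40% | 0.05% / 2% / 10% |
| One 10 mm lesion | about 30% | 51% | 62% | 0.05% / 2% / 10% |

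For two 15 mm nodes the floor changes nothing: about 9% either way at SD 1.5 if baseline readings are not restricted to entry size.

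**How much confirmation helps.** Over four scans, with baseline readings unrestricted, a stable 15 mm node gives at least one 20% rise in 26% / 56% / 72% of runs at SD 1.0 / 1.5 / 2.0, and a confirmed one in 4.4% / 17% / 29%. For a node that has shrunk from 15 to 8 mm, the figures are 50% / 69% / 78% and 13% / 26% / 35%. With a 5 mm floor the confirmed rates for the shrunken node fall to under 0.1%, 0.8% and 3.7%.

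**The case against.** Much of the case on the other side stands.

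- **Size of change.** A reader might infer that a 1 mm change is progression. That is true only when the whole nadir sum is 5 mm. The rule works on a sum of up to five target lesions plus new measurable ones: with five lesions at 5 mm, 1 mm is 4%.
- **Nodes and the default.** A reader might link the 5 mm default to small nodes. Appendix 3 does not support this, since nodes below 10 mm keep their actual measurement. A stable target node starts at 15 mm or more and needs a 3 mm rise, confirmed. Nodes are exposed only through the low relative threshold.
- **Best overall response.** A reader might expect irBOR to be fixed at irPD. SAP 10.4 allows that only for irPD within 12 weeks of first dose. With 8-weekly scans that means the first scheduled scan, when the nadir is still the baseline. A participant who later shrinks deeply has already reached at least irPR. The effect on irBOR is negligible.
- **Assumptions.** The rates depend on an assumed SD, a single lesion and 48 weeks of scans. At SD 0.5 mm over four scans, a stable 15 mm node is miscalled in under 0.1% of runs.
- **Missing text.** Under target disease, Appendix 3 has a stable category ("Stable: Does not qualify for CR, PR or Progression") but no separate progression entry in the text available. That may be a conversion loss, so nothing is inferred from it about intent.
- **Stakes.** irRECIST is secondary in Part B and exploratory in Part A. No hypotheses are tested, and RECIST 1.1 ORR is the main efficacy endpoint for Cohort 3B.
- **The 5 mm value.** The documents do not supply it. That it equals the default value does not make it a measurement-error threshold.

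None of this provides a floor. Appendix 4 states its own irPD rule, and that rule, as written, produces the events described.

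**Conclusion.** The point holds in a limited form. As written, a confirmed rise of less than 5 mm can be an irPFS event and end irDR whenever the nadir sum is below 25 mm. In practice this concerns mainly participants with one small or shrunken target lesion. The arithmetic is certain. The size is illustrative: with an assumed SD of 1.0 to 2.0 mm, six scans and baseline at or above entry size, confirmed irPD in an unchanged single lesion is about 7 to 40% (15 mm node) or about 30 to 62% (10 mm lesion), against about 0.05 to 10% with a 5 mm floor.

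It does not follow that stable small nodes are in general scored as progression, or that the primary safety endpoint, RECIST 1.1 ORR or irBOR is materially affected. It is worth settling before the irRECIST endpoints are derived.

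**What to change.** In SAP 10.4, for the derivation of irPFS and irDR, require both a rise of at least 20% over nadir and an absolute rise of at least 5 mm in the sum, at the first and at the confirming assessment. If the team prefers to keep the rule as written, report the version with the floor as a sensitivity analysis beside it. Identify 5 mm as a chosen value and fix it before the data are derived.

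Reconcile the wording of Appendix 3, Appendix 4 and Table 8 with the SAP. State whether the 5 mm default applies to the irRECIST sum, and which Table 8 row prevails when a sum is both 30% below baseline and 20% above nadir. Protocol Section 6.4.1 lists irRECIST progression among the reasons for withdrawal from treatment. The text should say that the floor applies to endpoint derivation only; no change to that section is proposed here.

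The cost is one clause and one programming condition on diameters already recorded. The downside is that true growth in very small sums is called slightly later.

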**Table 8. Overall Response Derived from Changes in Index, Non-index and New Lesions**

Measurable response	Non-measurable Response		Overall response using irRECIST b
Index and New Measurable Lesions (Tumor Burden) a	Non-Index Lesions	New Non-Measurable Lesions	
Decrease 100%	Absent	Absent	irCR
Decrease 100%	Stable	Any	irPR
Decrease 100%	Unequivocal progression	Any	irPR
Decrease $\geq 30\%$	Absent/stable	Any	irPR
Decrease $\geq 30\%$	Unequivocal progression	Any	irPR
Decrease $< 30\%$ and increase $< 20\%$	Absent/stable	Any	irSD
Decrease $< 30\%$ and increase $< 20\%$	Unequivocal progression	Any	irSD
Increase $\geq 20\%$	Any	Any	irPD

a. Decrease assessed relative to baseline.

b. Response (irCR and irPR) and progression (irPD) must be confirmed by a second, consecutive assessment at least 4 weeks apart.

## Appendix 5. Guidelines for Evaluation of Bone Scans

*Based on Prostate Cancer Working Group 3.*

An international expert committee of prostate cancer clinical investigators (the Prostate Cancer Clinical Trials Working Group 3 [PCWG3]) was reconvened and expanded and met in 2012-2015 to formulate updated criteria on the basis of emerging trial data and validation studies of the Prostate Cancer Clinical Trials Working Group 2 recommendations.

Given the frequency of bone involvement in patients with progressive, castration-resistant disease, the decreased emphasis of early changes in PSA, and the increased availability of cytostatic agents, reliable methods to assess changes in bone are of increasing importance. PCWG3 recognizes that standards for using MRI and PET to assess bone metastases are under active investigation, so only radionuclide bone scans are considered here. PCWG3 also recognizes that there are no validated criteria for response on radionuclide bone scan.

For control/relieve/eliminate end points, the PCWG3 recommends that post-treatment changes be recorded “no new lesions,” “new lesions” or “resolved bone lesion.” However, progression at the first scheduled assessment should be confirmed on a second scan performed 6 or more weeks later, in the absence of clearly worsening disease or disease-related symptoms. In the event of visible lesions disappearing, this should also be confirmed at the next scheduled assessment.

For prevent/delay end points, progressing disease on bone scan is considered when at least two new lesions relative to the first post-treatment scan is confirmed on a subsequent scan. PCWG3 does not recommend performing a follow-up bone scan before 12 weeks of treatment unless clinically indicated. At the first 12-week reassessment, defining disease progression requires a confirmatory scan (which shows additional new lesions compared with the first follow-up scan) performed 6 or more weeks later, because lesions visible at the first 12-week assessment may represent disease that was not detected on the pretreatment scan. When further progression is documented on the confirmatory scan, the date of progression recorded for the trial, is the date of the first scan that shows the change.

Nonmetastatic to metastatic progression: Any new unequivocal bone lesion, except if that lesion appears in the first post-treatment scan; in that case, document the event, continue treatment until 2 additional new lesions appear, and record both events.

**Appendix 6. National Cancer Institute (NCI) Common Terminology Criteria for Adverse Events (CTCAE)**

The NCI CTCAE (Version 4.03 dated June 14, 2010) has been placed in the Study Manual for this protocol. Alternatively, the NCI CTCAE may be reviewed on-line at the following NCI website: <http://ctep.cancer.gov/reporting.ctc.html>.

## Appendix 7. Management of Immune-related Adverse Events (irAEs) including Myasthenia Gravis

Note: References to study treatment in the table below refer to PF-06801591 and/or tremelimumab.

Gastrointestinal irAEs		
Severity of Diarrhea/Colitis (NCI-CTCAE v4)	Initial Management	Follow-up Management
Grade 1 Diarrhea: <4 stools/day over Baseline.  Colitis: asymptomatic.	-Continue study treatment.  -Symptomatic treatment (eg, loperamide).	-Close monitoring for worsening symptoms.  -Educate patient to report worsening immediately.  -If worsens: Treat as Grade 2, 3 or 4.
Grade 2 Diarrhea: 4 to 6 stools per day over Baseline; IV fluids indicated <24 hours; not interfering with ADL.  Colitis: abdominal pain; blood in stool.	-Withhold study treatment. -Symptomatic treatment.	-If improves to Grade $\leq 1$ : Resume study treatment.  -If persists >5-7 days or recurs: Treat as Grade 3 or 4.
Grade 3 to 4 Diarrhea (Grade 3): $\geq 7$ stools per day over Baseline; incontinence; IV fluids $\geq 24$ h; interfering with ADL.  Colitis (Grade 3): severe abdominal pain, medical intervention indicated, peritoneal signs.  Grade 4: life-threatening, perforation.	-Withhold for Grade 3. -Permanently discontinue study treatment for Grade 4 or recurrent Grade 3.  -1.0 to 2.0 mg/kg/day prednisone IV or equivalent.  -Add prophylactic antibiotics for opportunistic infections.  -Consider lower endoscopy.	-If improves: -Continue steroids until Grade $\leq 1$ , then taper over at least 1 month; resume study treatment following steroids taper (for initial Grade 3).  -If worsens, persists >3 to 5 days, or recurs after improvement: -Add infliximab 5 mg/kg (if no contraindication).  -Note: infliximab should not be used in cases of perforation or sepsis.

Dermatological irAEs		
Grade of Rash (NCI-CTCAE v4)	Initial Management	Follow-up Management
Grade 1 to 2 Covering $\leq$ 30% body surface area.	
 
-Continue study treatment.
 
-Symptomatic therapy (for example, antihistamines, topical steroids).
 
	
 
-If persists <math>>1</math> to 2 weeks or recurs:           
 
-Withhold study treatment.
 
-Consider skin biopsy.
 
 
 
-Consider 0.5-1.0 mg/kg/day prednisone or equivalent. Once improving, taper steroids over at least 1 month, consider prophylactic antibiotics for opportunistic infections, and resume study treatment following steroids taper.
 
-If worsens: Treat as Grade 3 to 4.
 

Grade 3 to 4 Grade 3: Covering $>$ 30% body surface area; Grade 4: Life threatening consequences.	
 
-Withhold study treatment for Grade 3.
 
-Permanently discontinue for Grade 4 or recurrent Grade 3.
 
-Consider skin biopsy.
 
-Dermatology consult.
 
-1.0 to 2.0 mg/kg/day prednisone or equivalent.
 
-Add prophylactic antibiotics for opportunistic infections.
 
	
 
-If improves to Grade <math>\leq</math>1:           
 
-Taper steroids over at least 1 month; resume study treatment following steroids taper (for initial Grade 3).
 
 
 

Pulmonary irAEs		
Grade of Pneumonitis (NCI-CTCAE v4)	Initial Management	Follow-up Management
Grade 1 Radiographic changes only.	
 
-Consider withholding study treatment.
 
-Monitor for symptoms every 2 to 3 days.
 
-Consider Pulmonary and Infectious Disease consults.
 
	
 
-Re-assess at least every 3 weeks
 
-If worsens: Treat as Grade 2 or Grade 3 to 4.
 

Grade 2 Mild to moderate new symptoms.	
 
-Withhold study treatment.
 
-Pulmonary and Infectious Disease consults.
 
-Monitor symptoms daily; consider hospitalization.
 
-1.0 to 2.0 mg/kg/day prednisone or equivalent.
 
-Add prophylactic antibiotics for opportunistic infections.
 
-Consider bronchoscopy, lung biopsy.
 
	
 
-Re-assess every 1 to 3 days If improves:
 
-When symptoms return to Grade <math>\leq 1</math>, taper steroids over at least 1 month, and then resume study treatment following steroids taper.
 
-If not improving after 2 weeks or worsening: Treat as Grade 3 to 4.
 

Grade 3 to 4 Grade 3: Severe new symptoms; New/worsening hypoxia; Grade 4: Life-threatening.	
 
-Permanently discontinue study treatment.
 
-Hospitalize.
 
-Pulmonary and Infectious Disease consults.
 
-1.0 to 2.0 mg/kg/day prednisone or equivalent.
 
-Add prophylactic antibiotics for opportunistic infections.
 
-Consider bronchoscopy, lung biopsy.
 
	
 
-If improves to Grade <math>\leq 1</math>:
 
-Taper steroids over at least 1 month.
 
-If not improving after 48 hours or worsening: Add additional immunosuppression (for example, infliximab, cyclophosphamide, IV immunoglobulin, or mycophenolate mofetil).
 

Hepatic irAEs		
Grade of Liver Test Elevation (NCI-CTCAE v4)	Initial Management	Follow-up Management
Grade 1 Grade 1 AST or ALT > ULN to 3.0 x ULN and/or Total bilirubin > ULN to 1.5 x ULN.	-Continue study treatment.	-Continue liver function monitoring. -If worsens: Treat as Grade 2 or 3 – 4.
Grade 2 AST or ALT >3.0 to ≤5 x ULN and/or total bilirubin >1.5 to ≤3 x ULN.	-Withhold study treatment.  -Increase frequency of monitoring to every 3 days.	-If returns to Grade ≤1: -Resume routine monitoring; resume study treatment.  -If elevation persists >5 to 7 days or worsens: -Treat as Grade 3 to 4.
Grade 3 to 4 AST or ALT >5 x ULN and/or total bilirubin >3 x ULN.	-Permanently discontinue study treatment.  -Increase frequency of monitoring to every 1 to 2 days.  -1.0 to 2.0 mg/kg/day prednisone or equivalent.  -Add prophylactic antibiotics for opportunistic infections. -Consult gastroenterologist/hepatologist.  -Consider obtaining MRI/CT scan of liver and liver biopsy if clinically warranted.	-If returns to Grade ≤1: -Taper steroids over at least 1 month.  -If does not improve in >3 to 5 days, worsens or rebounds: -Add mycophenolate mofetil 1 gram (g) twice daily.  -If no response within an additional 3 to 5 days, consider other immunosuppressants per local guidelines.

Renal irAEs		
Grade of Creatinine Increased (NCI-CTCAE v4)	Initial Management	Follow-up Management
Grade 1 Creatinine increased > ULN to 1.5 x ULN.	-Continue study treatment.	-Continue renal function monitoring. -If worsens: Treat as Grade 2 to 3 or 4.
Grade 2 to 3 Creatinine increased >1.5 and $\leq 6$ x ULN.	-Withhold study treatment.  -Increase frequency of monitoring to every 3 days.  -1.0 to 2.0 mg/kg/day prednisone or equivalent.  -Add prophylactic antibiotics for opportunistic infections.  -Consider renal biopsy.	-If returns to Grade $\leq 1$ : -Taper steroids over at least 1 month, and resume study treatment following steroids taper.  -If worsens: -Treat as Grade 4.
Grade 4 Creatinine increased $> 6$ x ULN.	-Permanently discontinue study treatment.  -Monitor creatinine daily.  -1.0 to 2.0 mg/kg/day prednisone or equivalent.  -Add prophylactic antibiotics for opportunistic infections Consider renal biopsy.  -Nephrology consult.	-If returns to Grade $\leq 1$ : Taper steroids over at least 1 month.

Cardiac irAEs		
Myocarditis	Initial Management	Follow-up Management
New onset of cardiac signs or symptoms and/or new laboratory cardiac biomarker elevations (eg, troponin, CK-MB, BNP) or cardiac imaging abnormalities suggestive of myocarditis.	
 
-Withhold study treatment.
 
-Hospitalize.
 
-In the presence of life threatening cardiac decompensation, consider transfer to a facility experienced in advanced heart failure and arrhythmia management.
 
-Consult cardiologist to establish etiology and rule-out immune-mediated myocarditis.
 
-Guideline based supportive treatment as per cardiology consult.*
 
-Consider myocardial biopsy if recommended per cardiology consult.
 
	
 
-If symptoms improve and immune-mediated etiology is ruled out, re-start study treatment.
 
-If symptoms do not improve/worsen, viral myocarditis is excluded, and immune-mediated etiology is suspected or confirmed following cardiology consult, manage as immune-mediated myocarditis.
 

Immune-mediated myocarditis.	
 
-Permanently discontinue study treatment.
 
-Guideline based supportive treatment as appropriate as per cardiology consult.* 1.0 to 2.0 mg/kg/day prednisone or equivalent.
 
-Add prophylactic antibiotics for opportunistic infections.
 
	
 
-Once improving, taper steroids over at least 1 month.
 
If no improvement or worsening, consider additional immunosuppressants (eg, azathioprine, cyclosporine A).
 

\*Local guidelines, or eg, ESC or AHA guidelines

ESC guidelines website: <https://www.escardio.org/Guidelines/Clinical-Practice-Guidelines> AHA guidelines website:

<http://professional.heart.org/professional/GuidelinesStatements/searchresults.jsp?q=&y=&t=1001>

Endocrine irAEs		
Endocrine Disorder	Initial Management	Follow-up Management
Grade 1 or Grade 2 endocrinopathies (hypothyroidism, hyperthyroidism, adrenal insufficiency, type I diabetes mellitus).	
 
-Continue study treatment.
 
-Endocrinology consult if needed.
 
-Start thyroid hormone replacement therapy (for hypothyroidism), anti-thyroid treatment (for hyperthyroidism), corticosteroids (for adrenal insufficiency) or insulin (for Type I diabetes mellitus) as appropriate.
 
-Rule-out secondary endocrinopathies (ie, hypopituitarism/hypophysitis).
 
	
 
-Continue hormone replacement/suppression and monitoring of endocrine function as appropriate.
 

Grade 3 or Grade 4 endocrinopathies (hypothyroidism, hyperthyroidism, adrenal insufficiency, type I diabetes mellitus).	
 
-Withhold study treatment.
 
-Consider hospitalization.
 
-Endocrinology consult.
 
-Start thyroid hormone replacement therapy (for hypothyroidism), anti-thyroid treatment (for hyperthyroidism), corticosteroids (for adrenal insufficiency) or insulin (for type I diabetes mellitus) as appropriate.
 
-Rule-out secondary endocrinopathies (ie, hypopituitarism/hypophysitis).
 
	
 
-Resume study treatment once symptoms and/or laboratory tests improve to Grade <math>\leq 1</math> (with or without hormone replacement/suppression).
 
-Continue hormone replacement/suppression and monitoring of endocrine function as appropriate.
 

Hypopituitarism/ Hypophysitis (secondary endocrinopathies).	
 
-If secondary thyroid and/or adrenal insufficiency is confirmed (ie, subnormal serum FT4 with inappropriately low TSH and/or low serum cortisol with inappropriately low ACTH): 
 
-Refer to endocrinologist for dynamic testing as indicated and measurement of other hormones (FSH, LH, GH/IGF-1, PRL, testosterone in men, estrogens in women).
 
-Hormone replacement/suppressive therapy as appropriate.
 
-Perform pituitary MRI and visual field examination as indicated.
 
 
 
-If hypophysitis is confirmed: 
 
-Continue study treatment if mild symptoms with normal MRI. Repeat the MRI in 1 month.
 
-Withhold study treatment if moderate, severe or life-threatening symptoms of hypophysitis and/or abnormal MRI. Consider hospitalization. Initiate corticosteroids (1 to 2 mg/kg/day prednisone or equivalent) followed by corticosteroids taper during at least 1 month.
 
-Add prophylactic antibiotics for opportunistic infections.
 
 
 
	
 
-Resume study treatment once symptoms and hormone tests improve to Grade <math>\leq 1</math> (with or without hormone replacement).
 
-In addition, for hypophysitis with abnormal MRI, resume study treatment only once shrinkage of the pituitary gland on MRI/CT scan is documented.
 
-Continue hormone replacement/suppression therapy as appropriate.
 

Other irAEs (not described above)		
Grade of other irAEs (NCI-CTCAE v4)	Initial Management	Follow-up Management
Grade 2 or Grade 3 clinical signs or symptoms suggestive of a potential irAE.	-Withhold study treatment pending clinical investigation.	-If irAE is ruled out, manage as appropriate according to the diagnosis and consider re-starting study treatment. -If irAE is confirmed, treat as Grade 2 or 3 irAE.
Grade 2 irAE or first occurrence of Grade 3 irAE.	-Withhold study treatment. -1.0 to 2.0 mg/kg/day prednisone or equivalent. -Add prophylactic antibiotics for opportunistic infections. -Specialty consult as appropriate.	-If improves to Grade $\leq 1$ : -Taper steroids over at least 1 month and resume study treatment following steroids taper.
Recurrence of same Grade 3 irAEs.	-Permanently discontinue study treatment. -1.0 to 2.0 mg/kg/day prednisone or equivalent. -Add prophylactic antibiotics for opportunistic infections. -Specialty consult as appropriate.	-If improves to Grade $\leq 1$ : Taper steroids over at least 1 month.
Grade 4.	-Permanently discontinue study treatment. -1.0 to 2.0 mg/kg/day prednisone or equivalent and/or other immunosuppressant as needed. -Add prophylactic antibiotics for opportunistic infections. -Specialty consult.	-If improves to Grade $\leq 1$ : Taper steroids over at least 1 month.
Requirement for 10 mg per day or greater prednisone or equivalent for more than 12 weeks for reasons other than hormonal replacement for adrenal insufficiency.  Persistent Grade 2 or 3 irAE lasting 12 weeks or longer.	-Permanently discontinue study treatment.  -Specialty consult.	

Abbreviations: ACTH=adrenocorticotropic hormone; ADL=activities of daily living; ALT=alanine aminotransferase; AST=aspartate aminotransferase; BNP=B-type natriuretic peptide; CK-MB=creatine kinase MB; CT= computed tomography; FSH=follicle-stimulating hormone; GH=growth hormone; IGF-1=insulin-like growth factor 1; irAE=immune-related adverse event; IV=intravenous; LH=luteinizing hormone; MRI=magnetic resonance imaging; NCI-CTCAE=National Cancer Institute-Common Terminology Criteria for Adverse Events; PRL=prolactin; T4=thyroxine; TSH=thyroid-stimulating hormone; ULN=upper limit of normal.

